#### 10.1.6. Month 36 (D1080) (±7 days)/End of Study/Early Termination

- Record of concomitant ocular and systemic medications [other than artificial tear (AT) usage]
- Urine pregnancy test (women of childbearing potential only)
- Record adverse events (AEs)
- Assessment of Artificial tears use by questioning the patient
- Symptoms evaluation by completing SANDE questionnaire
- Symptoms evaluation by completing the 0-4 point scale
- Quality of life questionnaires (DEQS)
- BCDVA

- Slit lamp examination
- TBUT
- Corneal and conjunctival fluorescein staining (modified Oxford scale)
- Schirmer test (without anaesthesia)
- IOP
- Collection of used/not used study medication containers and unpreserved artificial tear bottles
- Assessment of compliance to study medication
- Registration of End of Study or Early Termination in IWRS/IVRS Rave RTSM

#### 10.1.7. Unscheduled Visit

An Unscheduled visit will be performed if required between two scheduled visits (e.g. patient's request, check of medical event needed, but not for routine care that is not related to the protocol) and the reason for such a visit will be recorded in the CRF. In this case, the investigator will be asked to perform all the following procedures and examinations at his discretion (which must be performed in the chronological order defined below):

- Record of concomitant ocular and systemic medications [other than artificial tear (AT) usage]
- Record adverse events (AEs)
- Assessment of Artificial tears use by questioning the patient
- Symptoms evaluation by completing SANDE questionnaire
- Symptoms evaluation by completing the 0-4 point scale
- TBUT
- Corneal and conjunctival fluorescein staining (modified Oxford scale)
- IOP
- Collection of used/not used study medication containers and unpreserved artificial tear bottles, if any, or ask for patient's compliance with study medication regimen
- If needed, dispensation of study medication and unpreserved artificial tears for a 3-month period
- Patients will will be scheduled to return to the clinic at next planned scheduled visit

If necessary (e.g. to follow up an AE) the investigator may schedule further visits at his discretion.

In case of patient's premature study discontinuation:

- the investigator will be asked to perform all the examinations and assessments scheduled for the End of Study Visit (Month 36/Early Termination)
- the investigator will ensure that used and unused study medication for the study period has been collected from the patient by the appointed person at the study site

#### 11. ASSESSMENT OF EFFICACY

# 11.1. Corneal and Conjunctival Fluorescein Staining

Corneal and conjunctival fluorescein staining will be assessed immediately following the TBUT. Reading will be performed between 1 and 4 minutes after fluorescein instillation for the TBUT, to ensure that the dye does not diffuse into stroma blurring the discrete margin of any staining defects. The eye will then be examined at the slit lamp (16X magnification) using a yellow barrier filter and cobalt blue illumination to enhance visibility of staining.

Staining using fluorescein (provided by the Sponsor) will be graded using the modified Oxford scale (7-point ordinal scale, score 0, 0.5, and 1 to 5 per area [cornea + nasal and temporal conjunctiva]) for cornea and conjunctiva separately, see Appendix A-IV. On this modified scale, the score 0 corresponds to no staining dots and the score 0.5 corresponds to one staining dot per area.

A CFS grade of 0 represents complete corneal clearing.

A negative change score from baseline (Period 1) or from Month 12 (Period 2) will indicate improvement.

# 11.2. Tear Break-Up Time

Tear break-up time (TBUT) will be measured by determining the time to tear break-up. The TBUT will be performed after instillation of 2  $\mu$ l of 2% preservative-free sodium fluorescein solution (provided by the sponsor) into the inferior conjunctival cul-de-sac of each eye. To thoroughly mix the fluorescein with the tear film, the patient will be instructed to blink several times. In order to achieve maximum fluorescence, the examiner should wait approximately 30 seconds after instillation before evaluating TBUT. With the aid of a slit lamp at 10X magnification using cobalt blue illumination, the examiner will monitor the integrity of the tear film, noting the time it takes to form lacunae (clear spaces in the tear film) from the time that the eye is opened after the last blink. The TBUT will be measured twice during the first minute after the instillation of the fluorescein. If the 2 readings differ by more than 2 seconds, then a third reading will be taken.

The TBUT value will be the average of the 2 or 3 measurements.

A positive change from baseline (Period 1) or from Month 12 (Period 2) will indicate improvement.

#### 11.3. Schirmer Test (without anesthesia) (mm wetting/5min)

Schirmer test will be performed without anesthesia, 15 minutes after corneal fluorescein test. This test will be conducted in a dimly lit room. While the patient looks upwards, the lower lid will be drawn gently downwards and temporally. The rounded bent end of a sterile strip will be inserted into the lower conjunctival sac over the temporal one-third of the lower eyelid margin. The test should be done without touching directly the Schirmer test strip with the fingers to avoid contamination of skin oils. After 5 minutes have elapsed the Schirmer test strip will be removed and the length of the tear absorption on the strip will be measured.

A positive change from baseline (Period 1) or from Month 12 (Period 2) will indicate improvement.

# 11.4. Slit lamp examination

External ocular examination and undilated biomicroscopy will be performed using a slit lamp. The subject will be seated while being examined; grading of the Meibomian glands, lids, lashes, conjunctiva, tear film debris, anterior chamber and lens will be done according the scales in Appendix A-III.

#### 11.5. Use of Concomitant Artificial Tears

The use of artificial tears will be monitored over the course of the study for each patient. Patients will be asked about the average number of times per day artificial tears was used over the last week, and number of days they were not used during the week preceding the visits.

The Sponsor will provide unpreserved artificial tears for all the patients. After the Baseline Visit patients will be allowed to instill 1 unpreserved artificial tear drop, up to six instillations per day in each eye, to ameliorate their dry eye symptoms. Patients will be instructed not to use the unpreserved artificial tears within 30 minutes before or after the use of the study medication. Patients will also be instructed not to use the unpreserved artificial tears two hours before the scheduled study visit.

Patients will be instructed to return the used or not used unpreserved artificial tears at the scheduled study visits.

#### 11.6. Symptoms Evaluation (SANDE)

The self-administered Symptom Assessment iN Dry Eye (SANDE) questionnaire must be completed by the patient him/herself.

SANDE questionnaire will be used to score both severity and frequency of dry eye symptoms (see Appendix A-I). This 2-item frequency- and severity-based visual analogue scales (0-100mm VAS ranging respectively from" rarely" to "all the time", and from "very mild" to "very severe") is short and quick, and provides reliable measure for DED symptoms assessment. Symptoms will be evaluated for both eyes together.

A negative change from baseline (Period 1) or from Month 12 (Period 2) will indicate an improvement in dry eye disease symptoms.

## 11.7. Symptoms Evaluation Using 0-4 Point Scale

The 5-point Likert scales are a self-administered questionnaire and must be completed by the patient him/herself.

Burning/stinging, foreign body sensation, eye dryness, photophobia, pain and blurred/poor vision, will be assessed by the study patients using a 5-point Likert scale from none to very severe (0 to 4). Symptoms will be evaluated for both eyes together. (see Appendix A-II).

A decrease in symptom score from baseline (Period 1) or from Month 12 (Period 2) will indicate improvement of the symptom.

# 11.8. Quality of Life Questionnaires

### 11.8.1. Dry Eye symptoms-related Quality of Life Score (DEQS)

The DEQS consists of 15 items related to dry eye symptoms and influence on daily life, and the overall degree of Quality of Life impairment is calculated as a summary score (0 to 100).

The responses to DEQS are to be obtained from the patient through a self-administered format (completed by the patient him/herself). (see Appendix A-V).

#### 12. ASSESSMENT OF SAFETY

# 12.1. Safety Parameters

#### 12.1.1. Best Corrected Distance Visual Acuity (BCDVA)

Best corrected distance VA will be measured with the patient's best correction and recorded using a Snellen chart.

#### 12.1.2. Tonometry for measurement of Intraocular Pressure (IOP) (mmHg)

Investigator should use the same tonometer throughout the course of the study. Both eyes will be tested, with the right eye preceding the left eye. IOP will be assessed after completion of all other slit lamp examinations and dry eye assessments to avoid oxybuprocaine interference with the other examinations (Schirmer test especially) in case a tonometry measurement needs to be performed with an anesthetic.

All tonometers must be calibrated according to manufacturer's instructions.

#### 12.1.3. Adverse Events (AEs)

Adverse events, including ocular AEs, including the ocular complications, and systemic AEs will be recorded in the eCRFs. Any clinically significant change in concomitant disease or new concomitant conditions will be reported as AEs.

#### 12.1.4. Pregnancy Screen

Women of childbearing potential not using a medically acceptable, highly effective method of birth control (such as hormonal implants, injectable or oral contraceptives together with condoms, some intrauterine devices, sexual abstinence or vasectomized partner) from the Baseline Visit throughout the conduct of the study treatment periods and up to 2 weeks after the study end cannot be included in the study. Post-menopausal women (two years without menstruation) do not need to use any method of birth control. For women of childbearing potential only, urine hCG pregnancy tests will be performed during the course of the study, and they will receive continued guidance with respect to the avoidance of pregnancy, as part of the Schedule of Study Procedures

Patients must have a negative urine pregnancy test at Baseline and throughout the study.

### 12.2. Adverse Events and Other Safety Information

#### 12.2.1. Definitions

#### **12.2.1.1.** Adverse Event (AE)

An adverse event is any untoward medical occurrence in a clinical investigation subject administered a study drug. An AE does not necessarily have a causal relationship with the study drug. For this study, the study drugs are IKERVIS® and vehicle. Regardless of causality to the

study treatment, an AE can be an unintended sign (including an abnormal laboratory finding), symptom, or disease temporally associated with the use of study treatment.

Any significant change in a subject's condition from baseline, regardless of causality, is to be considered an AE (unless the change is determined to be a continuation of a pre-existing condition documented in the subject's medical history). A clinically significant worsening in severity, intensity, or frequency of a pre-existing condition may indicate an AE.

Worsening of findings e.g. in biomicroscopy from no findings to finding graded as moderate/severe, or change in grading from mild to severe, may be an indication of an AE. By investigator's judgment, also milder changes can be recorded as AEs.

An elective surgical procedure scheduled or planned prior to study entry is not considered an AE, and the underlying diagnosis for the procedure should be captured in the medical history as a pre-existing condition.

The lack of efficacy of the study treatment for the condition being investigated is not considered an AE unless a clinically significant change is assessed by the investigator.

Patients' answers given to study questionnaires (or changes in these) are not reviewed as basis for occurrence of AEs. However, the investigators will collect information on AEs at each subject contact by asking an open question on the subject's general health.

### 12.2.1.2. Serious Adverse Event (SAE)

A serious AE (SAE) may occur during any study phase (ie, baseline, treatment, or follow-up). SAE must fulfil one or more of the following criteria:

- Results in death
- It is immediately life-threatening\*
- It requires in-patient hospitalization or prolongation of existing hospitalization
- It results in persistent or significant disability or incapacity
- Results in a congenital abnormality or birth defect
- It is an important medical event that may jeopardize the patient or may require medical intervention to prevent one of the outcomes listed above (including sight-threatening\*\* events and cancer or neoplasm of any type).

\*Herein 'Life-threatening' refers to an event in which the patient was at immediate risk of death at the time of event; it does not refer to an event which hypothetically might have caused death.

\*\*Similarly 'Sight-threatening' refers to an event in which the patient was at immediate risk of losing sight; it does not refer to an event which hypothetically might have caused losing of sight.

Serious ocular adverse events include, but are not limited to the following adverse events which are considered to be sight-threatening and are to be reported as SAEs (medically important criteria):

- Adverse Events that caused a decrease in visual acuity > 6 lines (compared with the last assessment of visual acuity at the last visit)

- Adverse Events that caused a decrease in visual acuity to the level of Light Perception or worse
- Adverse Events that required surgical intervention or laser to prevent permanent loss of sight
- Adverse Events associated with severe intraocular inflammation (i.e., 3+ anterior chamber cell/flare or 3+ vitritis)
- Corneal perforation
- Adverse Events that, in the opinion of the investigator, may require medical intervention to prevent permanent loss of sight

#### 12.2.1.3. Case of Special Interest (CSI)

The following cases are considered to be of special interest by the sponsor:

- Non-serious AEs requiring (24 h) reporting to the sponsor:
  - Corneal ulceration
  - Decrease in visual acuity of 3 to 6 lines (compared with the last assessment of visual acuity at the last visit)
- Overdose of study drug
  - Administration of a quantity of a medicinal product exceeding the dose defined in the study protocol.
- Misuse of study drug
  - Situations where the medicinal product is intentionally and inappropriately used not in accordance with the study protocol.
- Medication error
  - Any unintentional error in the prescribing, dispensing, or administration of a medicinal product while in the control of the healthcare professional or patient.
- Abuse of study drug
  - Persistent or sporadic, intentional excessive use of medicinal product which is accompanied by harmful physical or psychological effects.

#### 12.2.1.4. Pregnancy Reports

It is required that women of childbearing potential are using a medically acceptable, highly effective method of birth control during the study and up to 2 weeks after the study end. Any pregnancy occurring during the study or within 14 days of completing the study should be reported to Santen EMEA Pharmacovigilance Unit (PVU) and the subject will be removed from the study.

Pregnancies of partners to study subjects with paternal drug exposure must also be reported to Santen EMEA PVII.

#### 12.2.2. Assessment of Adverse Events

All AEs (non-serious and serious) spontaneously reported by the subject and/or in response to an open question from the study personnel or revealed by observation will be recorded and assessed during the study at the investigational site. Regardless of relationship to the clinical study, all AEs that occur at any time from the point of signing of ICF to participate in the study until patient withdrawal or the scheduled exit visit must be recorded.

Information about all AEs will be collected from the signing of consent form until the end of the study. Even after completion of the study, the investigator shall notify Santen EMEA PVU of any new SAEs that may be associated with the study drug.

Non-serious AEs will be evaluated until recovery or until the last study visit. The investigator must follow up subjects with a SAE until it has resolved, stabilized or a final assessment can otherwise be done. The same principle applies to all study drug -related AEs which caused early termination and AEs which are under special interest.

The investigator will take appropriate and necessary therapeutic measures required for resolution of the AE. Any medication necessary for the treatment of a AE must be recorded. During the double-masked treatment period, the investigator should only unmask the treatment allocation if this is relevant to the safety of the subject.

During the study, patients will also be allowed to use unpreserved artificial tears provided by the Sponsor. The events with causal relationship to the artificial tears are considered as AEs.

#### 12.2.2.1. Seriousness

The seriousness of each AE must be assessed by the investigator according to the criteria set for SAEs in section 12.2.1.2. If the event does not meet the criteria of a SAE, it is assessed as non-serious.

#### 12.2.2.2. Causality to Study Drug or Artificial Tears

An investigator who is qualified in medicine must make the determination of causality to the study drug and artificial tears provided by the Sponsor for each AE occurred during the study as defined in section 12.2.2. The following categories shall be used:

**Related:** There is a reasonable possibility that the AE may have been caused by the study drug or artificial tears.

**Not related:** There is no reasonable possibility that the AE may have been caused by the study drug or artificial tears.

The investigator should decide whether, in his or her medical judgment, there is a reasonable possibility that the event may have been caused by the study drug or artificial tears. If no valid reason exists for suggesting a relationship, then the AE should be classified as "unrelated". If there is any valid reason, even if undetermined, for suspecting a possible cause-and-effect relationship between the study drug (or artificial tears) and the occurrence of the AE, then the AE should be considered "related".

#### 12.2.3. Relationship to Study Procedures

The relationship to study procedures (e.g., Schirmer test) should be determined for AE using the following categories:

**Related:** There is a reasonable possibility that an event may have been caused by a study procedure.

**Not Related:** There is no reasonable possibility that an event may have been caused by a study procedure.

#### 12.2.3.1. Severity of the Adverse Event

Severity (intensity) of the AE will be assessed according to the following scale:

- Mild: awareness of sign or symptom, but easily tolerated
- Moderate: discomfort sufficient to cause interference with normal activities
- Severe: incapacitating, with inability to perform normal activities

It is important to distinguish between serious and severe AEs. Severity is a measure of intensity whereas seriousness is defined by the criteria under Section 12.2.1.2. An AE of severe intensity may not be considered serious.

#### 12.2.3.2. Expectedness

AEs will be evaluated as to whether they are expected or unexpected. The assessment is performed by the sponsor and in this study it is based on the list of adverse reactions in the section 4.8 'Undesirable Effects' in the approved IKERVIS® EU Summary of Product Characteristics (SmPC) which acts as a Reference Safety Information (RSI).

- **Expected:** An AE is expected when the nature or severity of which is consistent with the applicable product information.
- **Unexpected:** An AE is unexpected when the nature or severity of which is not consistent with the applicable product information.

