#### 12.2.4.3. Expedited reporting

All SAE, CSI and Pregnancy reports must be reported to Santen EMEA PVU immediates but no later than within 24 hours of the first awareness of the event. The investigator must complete, sign and date the SAE (or CSI/Pregnancy) pages, verify the accuracy of the information recorded on the SAE (or CSI/Pregnancy) pages, and send a copy by e-mail or fax to Santen EMEA PVU:

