#### Santen EMEA, Pharmacovigilance Unit (PVU)

Email to [contact] or

Fax to [contact]

([contact])

The sponsor records all SAE, CSI and Pregnancy reports in the safety database of Santen.

Additional follow-up information, if required or available, should all be sent by e-mail or faxed to Santen EMEA PVU immediately but no later than within 24 hours of receipt and this should be completed on a follow-up SAE (or CSI/Pregnancy) form and placed with the original information and kept with the appropriate section of the eCRF and/or study file.

The sponsor is responsible for ongoing safety evaluation of the study drug. If there is at least a reasonable possibility that the event is related to the study drug and it is both serious and unexpected (SUSAR), the sponsor shall initiate expedited reporting according to applicable reporting requirements to all relevant parties, including regulatory authorities and ethics committees. Reporting responsibilities are described in the study specific safety management plan.

Investigators will also be notified of all suspected, unexpected serious study drug —related adverse reactions (SUSARs) that occur during the clinical trial.

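### Protocol 12.2.3.2: the Expected and Unexpected definitions overlap, so an adverse event that matches the product information on only one of nature and severity meets both, with no precedence rule

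*Protocol*

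**What the plan says.** Protocol 12.2.3.2 sets up a two-way classification: "AEs will be evaluated as to whether they are expected or unexpected". On who decides and against what, it says: "The assessment is performed by the sponsor and in this study it is based on the list of adverse reactions in the section 4.8" of the EU product characteristics for the drug, which serves as the reference safety information.

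It then gives two definitions:

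- The first, for the Expected class, reads "An AE is expected when the nature or severity of which is consistent with the applicable product information".
- The second, for the Unexpected class and evidently meant as the opposite of the first, reads "An AE is unexpected when the nature or severity of which is not consistent with the applicable product information".

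The classification is put to use in Protocol 12.2.4.3. If an event is at least possibly related to study drug and "it is both serious and unexpected (SUSAR), the sponsor shall initiate expedited reporting according to applicable reporting requirements to all relevant parties", authorities and ethics committees included. A separate sentence starts "Investigators will also be notified of all suspected, unexpected serious study drug" and covers the same class of reactions. That section also refers to a study-specific safety management plan for reporting responsibilities; the plan is not among the documents.

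The SAP neither defines nor uses expectedness. Its Section 9.2 tabulates adverse events, serious events, drug reactions and cases of special interest without it.

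**The concern.** The two sentences look like opposites but are not. The opposite of *nature or severity not consistent* is *nature and severity both consistent*. With *or* in both lines, some events satisfy both definitions, and the protocol does not say which prevails.

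The case that matters most is a reaction of a listed kind that is worse than the product information describes. It is expected because its nature matches, and unexpected because its severity does not. If such an event is also serious and related, the choice of line decides whether it counts as a SUSAR, and so whether the sponsor reports it on an expedited basis and tells the investigators. A definition with that role should give one answer for each event.

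**Working it through.** There is no figure in the plan to reproduce and no numerical input. The check is to list every combination under the two definitions.

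**Inputs, all from Protocol 12.2.3.2.** Let N mean that the nature of the event is consistent with the product information, and S that its severity is.

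- Expected as written: N or S.
- Unexpected as written: (not N) or (not S).
- Expected if *and* replaces *or*: N and S.

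| Nature consistent | Severity consistent | Expected as written | Unexpected as written | Expected with *and* |
|---|---|---|---|---|
| yes | yes | yes | no | yes |
| yes | no | **yes** | **yes** | no |
| no | yes | **yes** | **yes** | no |
| no | no | no | yes | no |

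**As written.** Each definition covers three of the four combinations. Since 3 + 3 = 6 and there are only 4 combinations, with none left uncovered, 6 − 4 = 2 are counted twice. These are the two middle rows.

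**With *and* in the Expected line only.** Expected covers one combination and Unexpected three. As 1 + 3 = 4, none falls in both and none falls in neither. Both middle rows become unexpected only.

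**Can severity differ within one listed reaction?** The protocol's own background suggests so. In Section 4.1.1, instillation site pain in the active arm of the 12-month pivotal trial was mild in 16.9%, moderate in 8.4% and severe in 3.9% of patients (together 29.2%, the total given there). This shows that one reaction term spans several severities. It does not show that any of those events was serious, or how the product information describes the reaction.

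**Which duties depend on the classification?**

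- Expedited reporting by the sponsor and notification of investigators (Protocol 12.2.4.3): these depend on it.
- Site-to-sponsor reporting of all serious events and cases of special interest, due "no later than within 24 hours of the first awareness of the event" (Protocol 12.2.4.3): this does not.
- Notification of serious adverse drug reactions to the IRB or IEC (Protocol 16.1): that sentence states no unexpectedness condition. It defers to local regulations and guidelines, which are not in the documents.

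**The case against.** A reader might infer that the protocol allows a SUSAR to go unreported. The text does not support that. The trigger in Protocol 12.2.4.3 is that an event is *unexpected*, not that it fails to be *expected*. The Unexpected definition is correctly worded: any mismatch in nature or severity suffices. A related, serious reaction that is worse than listed therefore meets the trigger, and the duty to report is stated as mandatory. Nothing exempts an event because it also fits the Expected line. This part of the objection stands. A report would be missed only if the sponsor let the looser sentence override the sound one.

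A reader might also infer that ethics committees would be left uninformed, or that SUSAR reporting is the only safeguard because no Data Monitoring Committee is planned (Protocol 13.7, SAP 5.5). That goes too far as well. Protocol 16.1 provides separately for notifying ethics committees. Protocol 12.2.1.2 makes corneal perforation and other sight-threatening events serious by rule, and 12.2.1.3 puts corneal ulceration and a loss of 3 to 6 lines of acuity on the 24-hour route. Protocol 12.2.4.3 makes the sponsor responsible for continuing safety evaluation. Because the sponsor assesses expectedness, no event is lost at site level through this wording.

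Finally, the safety management plan may contain a precedence rule, and the product information may say little about severity. Neither can be checked here. Both bear on how often the overlap would matter, but neither removes the contradiction from the protocol.

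**Conclusion.** The two definitions contradict each other for two of four combinations, and neither document resolves the overlap. This follows from the wording alone and needs no outside assumption. It is a drafting error in an operative rule, worth correcting because the classification governs expedited reporting.

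The consequence is a possibility and a limited one. It requires an event that is serious, related and matched on only one of nature and severity, and a sponsor that files it under the Expected line. The exposure then lies in the sponsor's expedited reporting and the notification of investigators. How many events could be affected cannot be derived: that depends on what the product information says about severity and on the content of the safety management plan. No endpoint, analysis population, sample size or error rate is affected.

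**What to change.** In Protocol 12.2.3.2, change *or* to *and* in the Expected definition, so that an event is expected only if both its nature and its severity are consistent with the product information. Leave the Unexpected definition as it is. The two are then exclusive and exhaustive, and no separate precedence statement is needed. Check that the safety management plan agrees.

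The change itself is one word (with the verb made plural) plus that check. The SAP needs no edit. The downside is at most some additional expedited reports, a number that the documents do not allow one to estimate.
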